6.1.2 DOSING AND ADMINISTRATION

The study is composed of 2 treatment arms:

- 1. Anakinra 100 mg/0.67 mL daily subcutaneous injection for 4 weeks on top of standard of care [active treatment];
- 2. Standard of care only [control group].

6.2 Preparation/Handling/Storage/Accountability

6.2.1 ACQUISITION AND ACCOUNTABILITY

Anakinra dispensed in small syringes (0.67 mL) will be provided to the patient for daily subcutaneous injection.

6.2.2 FORMULATION, APPEARANCE, PACKAGING, AND LABELING

Anakinra will be provided as commercially available Kineret[®] product.

6.2.3 PRODUCT STORAGE AND STABILITY

Anakinra should be stored in the refrigerator at 2 degrees C to 8 degrees C (36 degrees F to 46 degrees F). Anakinra should not be frozen or shaken. Anakinra should be protected from light.

6.2.4 PREPARATION

After completion of all baseline testing, patients randomized to anakinra will be given a 28-day supply of anakinra and will also receive instruction from the investigators regarding self-injection technique.

Adherence to the investigational treatment will be addressed by count of syringes and completion of all study visits. All concomitant medications will also be recorded at each clinic visit.

6.3 MEASURES TO MINIMIZE BIAS: RANDOMIZATION AND BLINDED ASSESSMENT

Randomization will be handled by a member of the research team not involved in the consenting process using a dedicated randomization algorithm, stratified by center (VCU / UMich) and by race/ethnicity (Caucasian / Others).

Assessment of ECG Holter and of imaging, for substudy, will be performed by operators who are blinded to treatment allocation.

6.4 STUDY INTERVENTION COMPLIANCE

Adherence to the investigational treatment will be addressed by count of syringes and completion of all study visits. All concomitant medications will also be recorded at each clinic visit.

6.5 CONCOMITANT THERAPY

All concomitant medications and dosages will be recorded at each clinic visit.

Patients may be on stable [at least 30 days] doses of steroids (< 0.5 mg/kg/day) or steroid-sparing agents including methotrexate but not tumor necrosis factor-alpha (TNF-alpha) blockers.

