4 STUDY DESIGN

4.1 OVERALL DESIGN

We designed a randomized open-label study of anakinra 100 mg daily once daily for 28 days on top of standard of care in patients with cardiac sarcoidosis, cardiac FDG uptake on PET scan, and CRP \geq 2 mg/L.

The study is composed of 2 treatment arms:

- 1. Anakinra 100 mg/0.67 mL daily subcutaneous injection on top of standard of care for 4 weeks [active treatment];
- 2. Standard of care only [control group].

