4.2 SCIENTIFIC RATIONALE FOR STUDY DESIGN

We chose to perform a pilot study a randomized, open label trial of 28 patients of anakinra 100 mg daily on top of standard of care versus standard of care only for 28 days to determine whether IL-1 blockade with anakinra is associated with a biological signal or not, based on surrogate endpoints of changes in systemic inflammatory biomarkers.

We believe that this small pilot study is a necessary initial step to determine feasibility and estimate the effect size of anakinra in a phase II study, to be followed by an appropriately powered multicenter RCT if the results of this pilot study prove promising.

This pilot study is structured to provide the necessary and sufficient information to make this determination.

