- No clinical findings characteristic of sarcoidosis are observed in any organs other than the heart. (The patient should be examined in detail for respiratory, ophthalmic, and skin involvement of sarcoidosis. When the patient is symptomatic, other etiologies that can affect the corresponding organs must be ruled out.)
- 4. ⁶⁷Ga scintigraphy or ¹⁸F-FDG PET reveals no abnormal tracer accumulation in any organs other than the heart.
- 5. A chest CT scan reveals no shadow along the lymphatic tracts in the lungs or no hilar and mediastinal lymphadenopathy (minor axis>10 mm).
- Histological diagnosis group Isolated cardiac sarcoidosis is diagnosed histologically when endomyocardial biopsy or surgical specimens demonstrate non-caseating epithelioid granulomas.
- (2) Clinical diagnosis group Isolated cardiac sarcoidosis is diagnosed clinically when criterion (d) and at least 3 other major criteria (a)-(e) are satisfied. (Table 1)

2. Cardiac fluoro-deoxyglucose uptake on recent PET (performed within the prior 60 days)

3. CRP high-sensitivity assay ≥2 mg/l (performed within the prior 60 days)

4. On stable medical therapy for cardiac sarcoidosis for at least 30 days prior to randomization

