6.5.1 RESCUE MEDICINE

The investigational treatment in this study is viewed as treatment to be added on top of current treatment on patients considered to be stable. If at any time, the subject requires intensification of the treatment for sarcoidosis including a drug that would be render the patient no longer a candidate for the study, the subject may choose to discontinue to study treatment and initiate the new treatment without delay. The subject may however not be able to continue the investigational drug treatment if a new immunosuppressive or biologic agent is added.

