7 STUDY INTERVENTION DISCONTINUATION AND PARTICIPANT DISCONTINUATION/WITHDRAWAL

7.1 DISCONTINUATION OF STUDY INTERVENTION

Reasons for discontinuation of treatment

Reasons for discontinuation of Anakinra:

- Systemic infection (sepsis)*;
- Surgery*;
- New diagnosis of cancer that requires local or systemic treatment;
- Hypersensitivity reaction (rash, anaphylaxis, arthritis);
- Severe injection site reactions*;
- Need for immunosuppressant therapy or treatment with a biologic agent (i.e. TNF-alpha blocker);
- Acute myocardial infarction or stroke*;
- Severe neutropenia (<1,000/mm3) if there is a perception of increased infectious risk by the provider*.

In the cases labelled by * treatment may be restarted by investigators after the condition is resolved.

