9.3 POPULATIONS FOR ANALYSES

We plan to compare the 2 groups (anakinra and control) in an intention-to-treat analysis by which all patients who (1) met all inclusion/exclusion criteria and (2) were randomly assigned to one of the 2 groups were considered as 'treated' independent of whether the patients assigned to anakinra received all or some or any of the investigational treatment after randomization has been completed and treatment assigned. For exploratory purposes we will also perform a per-protocol analysis in which the individual subjects not only will need to meet conditions (1) and (2) but also (3) need to have reported compliance with >75% of investigational drug prescribed.

Version 3.001 31 AUG 2021

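### Nothing clearly holds background steroid doses steady from randomization to the day-28 CRP in this open-label trial, and 9.3 lets patients be dropped from ITT after allocation is known (minor)

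*Combined protocol and SAP*

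**What the plan says.** Eligibility (5.1, item 4) requires the patient to be "On stable medical therapy for cardiac sarcoidosis for at least 30 days prior to randomization". The concomitant-therapy section (6.5) adds: "Patients may be on stable [at least 30 days] doses of steroids (< 0.5 mg/kg/day) or steroid-sparing agents", with TNF-alpha blockers not allowed. On follow-up, 6.5 says "All concomitant medications and dosages will be recorded at each clinic visit". Section 6.5.1 describes anakinra as "treatment to be added on top of current treatment on patients considered to be stable". It then deals with a patient who requires intensification or who receives a new immunosuppressive or biologic agent. Section 7.1 lists reasons for stopping anakinra.

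The design is open: "We designed a randomized open-label study of anakinra 100 mg daily once daily for 28 days on top of standard of care" (4.1). The blinding in 6.3 covers readers of the Holter and of the substudy imaging. It does not cover the clinicians who set steroid doses.

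The primary efficacy endpoint is the change in CRP from baseline to day 28 (9.1, 9.4.2), compared between arms by the time-by-group interaction. The sample size (9.2) assumes almost no change in CRP under standard of care alone. Change in the number and dose of sarcoidosis medicines is a secondary endpoint (1.1), with no time point attached.

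The intention-to-treat set (9.3) consists of patients who "met all inclusion/exclusion criteria and (2) were randomly assigned to one of the 2 groups".

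**The concern.** Stability is clearly required up to randomization, but the efficacy endpoint is measured over the four weeks that follow. A steroid taper or increase in those weeks could move CRP independently of anakinra. With allocation known, such changes need not be balanced. A clinician might taper a patient known to be on anakinra, or increase the dose in a control. Either would shrink the difference between arms. A taper in controls, or an increase on anakinra, would enlarge it.

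The sponsor's stated reason for item 4, in the summary of changes for the current version, is that changes in background therapy would influence the findings. That reason applies at least as strongly after day 1. The pilot is also meant to "determine feasibility and estimate the effect size of anakinra in a phase II study" (4.2), so a distorted CRP difference could carry into the planning of the next trial.

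The second issue is related. If a patient's earlier dose history is questioned after allocation is known, 9.3 makes failing item 4 a ground for leaving the intention-to-treat set. The decision to look, and the judgement reached, could both depend on the arm.

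**Working it through.** **1. What covers an existing steroid dose, and when**

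| Section | Before randomization | Day 1 to day-28 draw |
|---|---|---|
| 5.1 item 4 | Stable for at least 30 days | Silent |
| 6.5 | Bracketed 30 days matches item 4 | Doses recorded; *stable* might be meant to continue, but this is not stated |
| 6.5.1 | – | Required intensification and new agents; silent on tapers and elective changes of an existing dose |
| 7.1 | – | Reasons to stop anakinra; no rule on background dose |
| 9.4.1, 9.4.2 | – | CRP analysis does not mention background dose |

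No entry in the right-hand column clearly holds the dose. None expressly permits a discretionary change either.

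**2. The plan's own power figure**

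Inputs: 28 patients at 1:1, so 14 per arm (1.1, 6.1.1); mean CRP 7.64 mg/L, SD 3.74 mg/L and a 60% reduction (9.2). Two-sided alpha of 0.05 is assumed, since the documents do not state it.

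- Difference = 0.60 × 7.64 = 4.584 mg/L.
- SE = 3.74 × √(1/14 + 1/14) = 1.414 mg/L.
- Power = Φ(4.584/1.414 − 1.96) = 90.0%, against 90% in the 9.2 table.

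The table reproduces, so this point is not a criticism of the sample size. What matters is the input behind it: control-arm change close to zero. No conduct rule clearly supports that input.

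**3. Scale, for illustration only**

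Suppose *k* of 14 controls have a dose change that shifts their day-28 CRP by a fraction *f*, with no changes in the anakinra arm. Both *k* and *f* are assumptions.

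Shift in the arm difference = (k/14) × f × 7.64 mg/L; in percentage points of reduction, (k/14) × f.

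- Low: k = 1, f = 30%. Shift = 0.164 mg/L, or 2.1 points. A true 60% reduction would appear as 57.9% if CRP fell in that control, or 62.1% if it rose.
- High: k = 3, f = 50%. Shift = 0.819 mg/L, or 10.7 points. The same 60% would appear as 49.3% or 70.7%.

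The high case needs three changes in one arm, all in the same direction, and none in the other arm. These figures show only how the mechanism works. I draw no power or false-positive conclusion from them, because both driving inputs are invented.

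**4. The ITT definition**

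Take a randomised patient whose records later show a dose change 20 days before randomization. Item 4 is not met, so condition (1) of 9.3 fails and the patient leaves the intention-to-treat set, with the arm already known. If the set were all randomised patients, the same discovery would change nothing in the main analysis. The problem is selective removal, so a calculation of lost power would not measure it.

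**The case against.** The strongest reply is that the plan already means doses to be stable on study. Section 6.5 is the on-study concomitant-therapy section, it uses the word *stable*, and the summary of changes lists 5.1 and 6.5 together under the same rationale. Section 6.5.1 speaks of intensification that the patient *requires*, which suggests that elective changes were not contemplated. This carries weight. A reader might infer from the missing hold rule that discretionary tapers or increases are allowed in both arms. The documents do not support that; the wording is ambiguous. What survives is that two sites should not have to infer the rule.

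A second reply is that the comparison is anakinra plus standard of care against standard of care, so background adjustments are part of what is compared and are not all bias. This also stands in part. Clinically needed changes belong in the comparison, and the intention-to-treat analysis should keep the observed day-28 CRP. The reply is weaker for avoidable changes prompted by knowledge of the arm.

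Third, doses are recorded and medication change is a secondary endpoint, so changes up to day 28 can be tabulated by arm from planned data. Agreed: a dedicated table is a reporting detail.

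On 9.3, eligibility is checked at screening and again at randomization (1.3), so late discoveries should be uncommon. That limits how often the clause would be used, but it does not make the definition right.

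**Conclusion.** The point holds in two parts. For 6.5 it is a cheap improvement: stability is clear before randomization and unclear after it. For 9.3 it is a rule that is wrong as written, because an intention-to-treat set should not depend on an eligibility judgement that can be made after open allocation.

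The effect on the CRP comparison has unknown size and unknown direction. It is probably small. Patients enter after 30 stable days, the window is four weeks, 1.3 schedules no clinic visit between day 1 and day 28±3, and the primary objective is feasibility and tolerability. A reader might go further and conclude that the CRP result will be biased, or that its error rate is inflated by a stated amount. Nothing in the documents supports that, since they give neither a rate of dose change nor a steroid effect on CRP.

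Severity is minor. Confidence is moderate, because 6.5 may have been intended as an on-study rule.

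**What to change.** **6.5, add:** *Steroid and steroid-sparing doses are held constant in both arms from randomization through the day-28 blood draw unless a change is clinically needed; needed treatment is never delayed; the date, dose and reason for any change are recorded.*

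**9.3, edit:** define intention-to-treat as all randomised patients, analysed as assigned, and apply condition (1) to the per-protocol set only. The intention-to-treat analysis keeps the observed day-28 CRP whatever the background dose. The existing rule against imputing missing data (7.2, 7.3) is unaffected.

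**Optional:** repeat the CRP comparison without patients whose dose changed before the draw. This should be labelled descriptive, because the exclusion follows randomization.

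**Cost:** one sentence and one edited definition at the next amendment, plus one new data field, since 6.5 records medicines and doses but not the reason for a change. Some planned tapers would be deferred by up to four weeks, and a few referrals may be deterred. No extra visit or blood draw is needed. The rule removes only avoidable changes; clinically needed ones will still occur and will still count.

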6.5.1 RESCUE MEDICINE

The investigational treatment in this study is viewed as treatment to be added on top of current treatment on patients considered to be stable. If at any time, the subject requires intensification of the treatment for sarcoidosis including a drug that would be render the patient no longer a candidate for the study, the subject may choose to discontinue to study treatment and initiate the new treatment without delay. The subject may however not be able to continue the investigational drug treatment if a new immunosuppressive or biologic agent is added.

7 STUDY INTERVENTION DISCONTINUATION AND PARTICIPANT DISCONTINUATION/WITHDRAWAL

7.1 DISCONTINUATION OF STUDY INTERVENTION

Reasons for discontinuation of treatment

Reasons for discontinuation of Anakinra:

- Systemic infection (sepsis)*;
- Surgery*;
- New diagnosis of cancer that requires local or systemic treatment;
- Hypersensitivity reaction (rash, anaphylaxis, arthritis);
- Severe injection site reactions*;
- Need for immunosuppressant therapy or treatment with a biologic agent (i.e. TNF-alpha blocker);
- Acute myocardial infarction or stroke*;
- Severe neutropenia (<1,000/mm3) if there is a perception of increased infectious risk by the provider*.

In the cases labelled by * treatment may be restarted by investigators after the condition is resolved.

7.2 PARTICIPANT DISCONTINUATION/WITHDRAWAL FROM THE STUDY

Patient withdrawal

Patients may withdraw from the study at any time. The investigators can withdraw any patient at any time from the study if medically necessary. Missing data will not be inputted. The decision regarding continuation or termination of the study will be solely based on safety data. Interim analyses will be performed by the DSMB as indicated below.

It will be documented whether or not each patient completed the study. If for any reason the study treatment or observations were discontinued, the reasons will be recorded and the IRB will be informed.

Reasons for early termination of the study

The decision regarding continuation or termination of the study will be solely based on safety data, and will be made by the DSMB. Interim analyses will be performed by the DSMB.

Halting rules

The study will be temporarily suspended if any of the following conditions are met:

• Any serious adverse event that probably or definitely related to the investigational product;

- The number of subjects experiencing a *serious* adverse event considered *unrelated or only possibly related* to the investigational product exceeds 50% (after the first 3 or more subjects are enrolled);
- The number of subjects experiencing either a serious adverse event considered unrelated or only possibly related to the investigational product or a non-serious adverse event of at least moderate intensity that is probably or definitely related to the investigational product exceeds 75%.

If any of these conditions are met, the enrollment is halted until the DSMB is given the opportunity to review the data. After the assessment of the DSMB, a discussion with the PI and the Sponsor (NCATS) should be held prior to the final decision to resume or permanently stop the study.

Example of data provided to the DSMB:

- [____] of subjects with serious AE considered probably or definitely related, if >0, halting rule
- [____] of subjects with serious AE considered unrelated or only possibly related, if >50%, halting rule
- [____] of subjects with serious AE unrelated or only possibly related + [_____] number of subjects with nonserious AE of at least moderate intensity probably or definitely related, if >75%, halting rule

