8.3.3.2 RELATIONSHIP TO STUDY INTERVENTION

All adverse events (AEs) must have their relationship to study intervention assessed by the clinician who examines and evaluates the participant based on temporal relationship and his/her clinical judgment. The degree of certainty about causality will be graded using the categories below. In a clinical trial, the study product must always be suspect.

Definitely related: The event is temporally related to the administration of the study intervention and, in the opinion of the investigator, no other etiology explains the event.

Probably related: The event is temporally related to the administration of the study intervention and represents, in the opinion of the investigator, the most plausible explanation of the event.

Possibly related: The event is temporally related to the administration of the study intervention but, in the opinion of the investigator, it does not represent the most likely explanation of the event.

Definitely Unrelated: The event is temporally independent of study intervention and/or the event appears, in the opinion of the investigator, to be explained by another etiology.

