8.3.6 SERIOUS ADVERSE EVENT REPORTING

The MAGiC ART is an investigator-initiated study in which, for the purpose of the FDA, the investigator is also the sponsor.

The study is conducted under 21 CFR 312.2(b) regulation for IND exemption (as indicated by pre-IND inquiry 142352 of December 19, 2018 to [name])

All **co-investigators will be instructed to immediately report to the PI (functioning as PI/Sponsor) of** any serious adverse event, whether or not considered study intervention related, including those listed in the protocol or investigator brochure and must include an assessment of whether there is a reasonable possibility that the study intervention caused the event.

The PI/Sponsor is responsible to determine if the criteria for reporting to the DSMB/NCATS/FDA are met. The PI/Sponsor is also responsible for following all serious adverse events (SAEs) until satisfactory resolution or until the site investigator deems the event to be chronic or the participant is stable.

The PI/Sponsor will be responsible for notifying the DSMB, NCATS, IRB and the Food and Drug Administration (FDA) of any unexpected fatal or life-threatening **suspected adverse reaction** as soon as possible, but **in no case later than 7 calendar days**.

The PI/Sponsor must report any suspected adverse reaction that is both serious and unexpected.

The sponsor must report an adverse event as a suspected adverse reaction only if there is evidence to suggest a causal relationship between the drug and the adverse event, examples are: (A) A single occurrence of an event that is uncommon and known to be strongly associated with drug exposure (e.g., angioedema, hepatic injury, Stevens-Johnson Syndrome); (B) One or more occurrences of an event that is not commonly associated with drug exposure, but is otherwise uncommon in the population exposed to the drug (e.g., tendon rupture); (C) An aggregate analysis of specific events observed in a clinical trial (such as known consequences of the underlying disease or condition under investigation or other events that commonly occur in the study population independent of drug therapy) that indicates those events occur more frequently in the drug treatment group than in a concurrent or historical control group."

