9.4.4 SAFETY ANALYSES

The DSMB will monitor the progress of the present trial. The DSMB will meet regularly to review safety data every 6 months or sooner in case of a serious unexpected adverse event that is considered to be possibly, probably or definitely related to the research. All meetings, and specifically any action taken by the committee and the reasons for the actions, will be recorded. These documents will include any data summaries or analyses provided to the DSMB and will remain confidential until the study is concluded. No interim efficacy analyses are planned.

Interim safety analyses will, however, be performed at each meeting. The DSMB will be provided with data related to adverse events. The DSMB may choose to stop enrollment on the basis of safety data observed. If safety concerns are found, further enrollment will not be allowed until issues are resolved. If no safety concerns are found, enrollment will continue until the target sample size is reached. The following pre-specified halting rules are provided to the DSMB as guidance.

Example of data provided to the DSMB:

- [____] of subjects with serious AE considered probably or definitely related, if >0, halting rule
- [____] of subjects with serious AE considered unrelated or only possibly related, if >50%, halting rule
- [____] of subjects with serious AE unrelated or only possibly related + [_____] number of subjects with nonserious AE of at least moderate intensity probably or definitely related, if >75%, halting rule

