10.1.7 CLINICAL MONITORING

The DSMB will monitor the progress of the present trial. The DSMB will meet regularly to review safety data every 6 months or sooner in case of a serious unexpected adverse event that is considered to be possibly, probably or definitely related to the research.

All meetings, and specifically any action taken by the committee and the reasons for the actions, will be recorded. These documents will include any data summaries or analyses provided to the DSMB and will remain confidential until the study is concluded. No interim efficacy analyses are planned.

Interim safety analyses will, however, be performed at each meeting. The DSMB will be provided with data related to adverse events. The DSMB may choose to stop enrollment on the basis of safety data observed. If safety concerns are found, further enrollment will not be allowed until issues are resolved.

If no safety concerns are found, enrollment will continue until the target sample size is reached. The following pre-specified halting rules are provided to the DSMB as guidance.

Halting rules

The study will be temporarily suspended if any of the following conditions are met:

- Any serious adverse event that probably or definitely related to the investigational product;
- The number of subjects experiencing a *serious* adverse event considered *unrelated or only possibly related* to the investigational product exceeds 50% (after the first 3 or more subjects are enrolled);
- The number of subjects experiencing either a serious adverse event considered unrelated or only possibly related to the investigational product or a non-serious adverse event of at least moderate intensity that is probably or definitely related to the investigational product exceeds 75%.

If any of these conditions are met, the enrollment is halted until the DSMB is given the opportunity to review the data and consider the request for unblinding. After the assessment of the DSMB, a discussion with the PI and the Sponsor (NCATS) should be held prior to the final decision to resume or permanently stop the study.

Example of data provided to the DSMB:

- [____] of subjects with serious AE considered probably or definitely related à if >0 --> halting rule
- [____] of subjects with serious AE considered unrelated or only possibly related à if >50% --> halting rule

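### The two percentage halting rules name no denominator and read as pooling both arms: at full balanced enrollment, possibly related SAEs in all 14 anakinra subjects and no controls would trigger neither

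*Combined protocol and SAP*

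**What the plan says.** Section 7.2, repeated in 10.1.7, gives three halting rules.

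- Rule 1: any SAE probably or definitely related to the product.
- Rule 2: the number of subjects with an SAE unrelated or only possibly related "to the investigational product exceeds 50% (after the first 3 or more subjects are enrolled").
- Rule 3: the number of subjects with either a rule 2 event or "a non-serious adverse event of at least moderate intensity that is probably or definitely related to the investigational product exceeds 75" per cent.

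Neither percentage rule names an arm. The example DSMB data lines in 7.2, 9.4.4 and 10.1.7 carry one unsplit count per category, for instance "of subjects with serious AE considered unrelated or only possibly related, if >50%, halting rule". Allocation is 1:1 with 28 subjects (1.1, 6.1.1), and the second arm is "Standard of care only [control group"] (4.1).

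The surrounding oversight matters here. Section 9.4.4 says: "The following pre-specified halting rules are provided to the DSMB as guidance". Sections 9.4.4 and 10.1.7 convene the DSMB before its six-monthly meeting for a serious unexpected event that is possibly, probably or definitely related, and 10.1.6 is similar. Section 10.1.6 also has the DSMB review data on each arm, lets it halt the study by a vote of three members, and leaves the data elements to a charter.

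**The concern.** Only subjects given anakinra can be harmed by it. If the percentages are taken over everyone enrolled, controls dilute a drug effect by about half.

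Rule 1 does not fully cover this, because it depends on attribution case by case. Under 8.3.3.2 an event is only possibly related when, in the investigator's opinion, "it does not represent the most likely explanation of the event". Serious infection in a patient on steroids or methotrexate can fairly be graded that way, so a drug excess may show only when the arms are compared. Section 8.3.6 accepts this kind of evidence for FDA reporting, namely that "those events occur more frequently in the drug treatment group than in a concurrent or historical control group". No halting rule uses it.

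Blinding would be a reason to pool, but the trial is open-label. Section 10.1.7 still gives the DSMB the "opportunity to review the data and consider the request for unblinding", which suggests that the rules were not revisited when the design changed.

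At stake is how many subjects start anakinra before a prespecified trigger acts. Tolerability is part of the primary objective (section 3), and no targeted anti-IL-1 therapy has been tested in this disease (2.3.3).

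**Working it through.** The plan gives no derivation or operating characteristics for the 50% and 75% thresholds, so there is no figure of its own to reproduce.

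**Which denominator.** Three signs point to all enrolled subjects: rule 2 starts from a count of subjects enrolled, both rules count unrelated SAEs (which occur in either arm), and the template lines are unsplit. This is an inference from the text.

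**Counts at full enrollment (14 + 14).**
- Rule 2 needs more than 0.50 × 28 = 14, so 15 subjects. All 14 anakinra subjects and no controls give 14/28 = 50.0%: no trigger.
- Rule 3 needs more than 0.75 × 28 = 21, so 22 subjects. All 14 anakinra subjects leave 22 − 14 = 8 controls who must have an SAE. P(at least 8 of 14 controls) is 9e-8, 1.7e-5 and 0.0024 at assumed control SAE risks of 5%, 10% and 20%.

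**Expected share for rule 2.** With anakinra and control SAE risks pA and pC, the pooled share is (pA + pC)/2. It exceeds 0.50 only if pA > 1 − pC, that is above 95%, 90% or 80% at pC = 5%, 10% or 20%.

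**Exact chance of exceeding 50% at full enrollment, pC = 10% (assumed).**

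| pA | pooled (15 or more of 28) | anakinra arm (8 or more of 14) |
|---|---|---|
| 50% | 0.3% | 39.5% |
| 60% | 1.4% | 69.2% |
| 70% | 5.1% | 90.7% |
| 80% | 15.0% | 98.8% |

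**During accrual.** Small early denominators can cross the line by chance, so the full-enrollment table overstates the gap. A simulation covers this. Inputs: 28 subjects, 16 to 20 enrolled per year (8 to 10 per site, 5.5), a 10% background SAE risk over 180 days, a drug-caused SAE with probability d = 0.50 at a uniform time on days 1 to 28, and rules checked at each event. The total anakinra SAE risk is then 1 − 0.90 × 0.50 = 55%. The table gives the chance of a halt before enrollment ends, with rule 1 active, by the share of drug-caused SAEs graded probable or definite.

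| share graded probable or definite | rules as written, pooled | both percentages on anakinra subjects (minimum 3) |
|---|---|---|
| 0% | 31% | 78% |
| 10% | 63% | 86% |
| 20% | 82% | 92% |

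The difference falls from 47 points to 23 and then 10. The full gain therefore needs every drug-caused SAE to escape rule 1.

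**The case against.** The strongest reply is that other provisions cover most of the ground.

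- **Early meetings.** A single unexpected SAE that is even possibly related brings the DSMB together, and the board can stop enrollment. Under 8.3.3.3 an event is unexpected if its nature, severity or frequency does not match the described risks. Arrhythmia is not among the listed anakinra risks (2.3.1), so a possibly related arrhythmic SAE would call the board. Unanticipated problems also reach the IRB and DSMB within 5 days (8.4.2). This stands. A reader might infer that possibly related SAEs wait for the six-monthly meeting; the documents do not support that.
- **Rule 1.** Section 8.3.3.2 says the study product must always be suspect, and an open-label assessor knows the arm. Grading no drug-caused SAE as probable is the extreme case. This stands, and the second table shows its effect.
- **Remote rates.** The protocol cites serious infection at 1.8% versus 0.6%, and no issues with severe infections in over 200 patients (2.3). An anakinra SAE rate of 55% is far from that. It stands as a caution, although a halting rule set at 50% is meant for that range.
- **Denominator not stated.** The charter is not in these documents and may define it, and the templates are labelled as examples. This stands; a sentence in the protocol would settle it.
- **Pooled rule 2 as a trial-wide alarm.** This is reasonable, and the fix keeps it.

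**Conclusion.** The point holds as a minor gap in the prespecified triggers. Read naturally, rules 2 and 3 pool the arms. At full balanced enrollment, rule 2 is not met by SAEs in every anakinra subject alone, and rule 3 cannot be met by drug harm alone. This structural result needs no assumed event rate; it rests on the pooled reading and 14 per arm.

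The size of the practical gap does depend on assumptions. It mainly concerns three kinds of event in excess on anakinra: expected SAEs graded possibly related (serious infection is the obvious case), SAEs graded unrelated, and related non-serious events of at least moderate intensity. The 31% versus 78% contrast applies only if no drug-caused SAE is graded probable or definite, at assumed rates of 10% background and 50% drug-caused.

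Two stronger readings are tempting. One is that the trial could not halt for harm on anakinra. Rule 1, early chance crossings of rule 2 and the DSMB's own vote all contradict that. The other is that nobody compares the arms; 10.1.6 says the DSMB reviews each arm. No efficacy estimate is affected.

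**What to change.** In 7.2 and 10.1.7:

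1. Keep rule 2 over all enrolled subjects, and say so.
2. Add the same threshold, more than 50%, among subjects assigned to anakinra once at least 3 of them are enrolled.
3. Apply rule 3's 75% to subjects assigned to anakinra, with a minimum of about 6.
4. Split each DSMB template line (7.2, 9.4.4, 10.1.7) into anakinra and control counts.

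If the charter already fixes the denominator, state it in the protocol.

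The change takes a few words and one template column, with no new data. False pauses on SAEs rise slightly: about 2% versus 1% at a 10% SAE risk in both arms, and 7% versus 4% at 20%, computed with a minimum of 3.

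Rule 3 would pause more often only if moderate related reactions are common. If half of anakinra subjects had one (50% is the protocol's upper figure for any injection-site reaction) and SAE risk were 10%, applying both percentages to anakinra subjects with a minimum of 3 would pause 24–26% of trials, against 8–11% as written. With a minimum of 6, rule 3 alone would pause about 17–18%. At reaction risks of 25% and 10%, even a minimum of 3 gives 3–4% and about 1%, against 4–6% and 2–3% as written. A pause only holds enrollment for DSMB review.
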